6.2 Dose escalation

- 6.2.1. The proposed study will follow a phase IA-B dose-escalation design wherein three SBRT dose levels targeting the primary tumor will be evaluated; level I: 6 Gy x 5 fractions (a common palliative dose), level II: 8 Gy x 5 fractions and level III: 10 Gy x 5 fractions (a common definitive dose).
- 6.2.2. Dose-limiting toxicity (DLT) will be defined as any grade 4 or higher toxicity that occurs within 30 days post MWA (approximately 90 days post SBRT) specifically: hemorrhage, hematoma, nephrotoxicity, gastric, duodenal or small bowel perforation or obstruction attributable to the radiation, the MWA or the combination of the treatment. Attributable DLT will be defined as that which is possibly, probably or definitely felt to be due to either radiation or ablation and occurring within the vicinity of the radiation treatment field (as reviewed by Drs. [name]/[name]) or in the vicinity of the microwave ablation (as reviewed by [name]). Grade 3 toxicity is not considered a DLT as it may be seen in routine, standard of care treatment. If progressive disease is found at the time of interval imaging and the patient is deemed ineligible for MWA, the patient will not be part of the cohort used for DLT analysis as his/her inclusion may falsely lower potential toxicity rates.
- 6.2.3. A standard, traditional 3+3 design will be utilized for dose escalation (Figure). For each three patient cohort, DLT will be assessed. In the case of 0/3 DLTs, the dose will be escalated to the next level. In the case of 2/3 DLTs, the dose escalation will be halted with the previous level being the MTD. In the case of 1/3 DLTs, an additional three patients will be enrolled at the current dose level. If no additional DLTs are seen, the dose will be escalated to the next level. In the event of a total of 2 or more DLTs in 6 patients, the dose escalation will be halted with the previous dose level being the MTD. Once the MTD has been established, the MTD will be used for the subsequent Phase IB expansion cohort.

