- 6.2.4. Dose escalation/de-escalation will continue until a maximum of 18 patients are accrued or dose-level I is shown to exceed the MTD. To allow efficient conduct of the study without compromising patient safety, accrual in the phase-IA study will be done in groups of three patients, with subsequent dose level accrual only after the occurrence of DLT thirty days after ablation has been evaluated for all at the current dose level. The phase-IB portion of the trial will consist of an additional ten patients (for a theoretical maximum of 28 total patients) to validate the results of phase-IA and provide a preliminary assessment of efficacy.

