6.9 Criteria for Removal from Treatment

A patient's ongoing treatment on protocol will be temporarily or permanently withheld if any of the events below occur:

- 6.9.1. Illness that prevents further administration of treatment
- 6.9.2. Radiation dose constraints that are unable to be met at the current dose level.
- 6.9.3. DLTs or other unacceptable adverse events

- 6.9.4. Patient decision to withdraw from study
- 6.9.5. General or specific changes in patient's condition render the patient unacceptable for further treatment in the judgment of the treating physician or the study investigators

The reason for treatment stop/study removal and the date will be documented in a Case Report Form.

7. Measurement of Treatment

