2. Is life threatening (places the subject at immediate risk of death)
3. Requires inpatient hospitalization or prolongation of existing hospitalization
4. Is a persistent or significant disability/incapacity
5. Is a congenital anomaly/birth defect
6. Any event that does not exactly meet this definition yet, in the investigator's opinion represents a significant hazard can be assigned the "other significant hazard" regulatory reporting serious criteria
7. Additionally, important medical events that may not be immediately life threatening or result in death or hospitalization but that may jeopardize the subject or require intervention to prevent one of the outcomes listed above, or result in urgent investigation, may be considered serious. Examples include allergic bronchospasm, convulsions, and blood dyscrasias.

Note: All deaths on treatment require both routine and expedited reporting regardless of causality. Attribution to treatment or other cause must be provided. "On treatment" is defined as during or within 30 days of completing protocol treatment (MWA).

All serious adverse events deemed to be related by the investigator to the SBRT or MWA (as listed in section 13.) will be collected and recorded throughout the study period beginning with the signing of the informed consent through the day patient is removed from the study or the date of death or three years after completion of the MWA (or the last SBRT treatment if surgery is not performed), whichever is earlier.

All serious adverse events that occur after the subject has signed the informed consent form must be reported to University of Wisconsin Carbone Cancer Center Data Safety and Monitoring Board and other regulatory agencies.

Serious adverse events occurring after conclusion of the study AND thought to be possibly related to the investigational study will be collected and reported within 10 working days of discovery or notification of the event via the same mechanism.

Table 3. Expedited reporting requirements for adverse events that occur within 30 days of the last protocol intervention.

FDA Reporting Requirements for Serious Adverse Events (21 CFR Part 312)
--

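### The DLT-cohort exclusion covers only progressors ineligible for MWA; the plan does not say how other DLT-free patients who miss MWA enter the 3+3 count

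*Combined protocol and SAP*

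**What the plan says.** The primary objective (3.2) is the MTD of SBRT followed by MWA. Sections 6.2.2, 7.1.1 and 9.3.1 all close the DLT window 30 days after ablation. Section 6.2.2 counts events "attributable to the radiation, the MWA or the combination of the treatment", so radiation alone can cause a DLT.

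Section 6.2.2 names one exclusion from the DLT cohort: "If progressive disease is found at the time of interval imaging and the patient is deemed ineligible for MWA", then "the patient will not be part of the cohort used for DLT analysis as his/her inclusion may falsely lower potential toxicity rates".

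Other sections foresee SBRT without MWA:

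- Section 6.9 lists "Illness that prevents further administration of treatment", withdrawal, changes in the patient's condition, and adverse events that are unacceptable without being DLTs.
- Section 6.1 uses interval imaging to check that MWA is still feasible.
- Section 13.4 runs SAE collection from the MWA, "or the last SBRT treatment if surgery is not performed".

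Section 6.2.4 allows "subsequent dose level accrual only after the occurrence of DLT thirty days after ablation has been evaluated for all at the current dose level". Sections 6.2.3, 9.4.1 and 13.5.1 state the rules for cohorts of three and six without saying which patients make up those numbers.

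**The concern.** The bias that 6.2.2 guards against comes from the missing MWA, not from the progression. A patient who never has the ablation is not exposed to its hemorrhage, hematoma and nephrotoxicity risk on top of SBRT, whatever the reason. The plan accepts this principle and applies it to one route only.

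The toxicity route deserves particular attention. Section 6.2.2 says grade 3 toxicity is not a DLT, so a patient kept from MWA by grade 3 SBRT toxicity could enter the count as a success for the combination.

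The stated exclusion is itself incomplete in two ways. It leaves two patients in a cohort of three, and no replacement rule says what follows. It also makes no exception for a progressor who has already had a DLT attributable to SBRT, so a real event would leave the count.

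At stake is the denominator of the primary endpoint. In a cohort of three, one patient is a third of the evidence, and the resulting MTD sets the Phase IB dose (6.2.3, 9.1.2.1).

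**Working it through.** **The plan's own figures.** Three levels of 3 patients give 9, three levels of 6 give 18, and 18 + 10 = 28. The stated 9-18 and 28 reproduce, with no allowance for non-evaluable patients. MWA at 8 weeks plus 30 days is 56 + 30 = 86 days after SBRT, which matches the approximate 90 days in 6.2.2.

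**What happens to a DLT-free patient who misses MWA.**

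| Reason | Handling in the plan |
|---|---|
| Progression and ineligible for MWA | Out of the DLT cohort (6.2.2); replacement not stated |
| Illness, change in condition, non-DLT toxicity | Treatment stops (6.9); DLT cohort status not stated |
| Withdrawal | As above; after non-treatment-related withdrawal, study data collection also stops (6.8) |
| MWA infeasible without progression | Checked at interval imaging (6.1); DLT cohort status not stated |

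**Effect if such a patient is counted.** The documents give no true DLT rate for the combination (p), no rate for SBRT alone and no missed-MWA rate, so all of these are assumptions. Under 6.2.3:

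P(pass) = P(0 of 3) + P(1 of 3) × P(0 of next 3).

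- All ablated: P(pass) = (1−p)³ + 3p(1−p)² × (1−p)³.
- One of the first three unablated at zero risk, next three all ablated: P(pass) = (1−p)² + 2p(1−p) × (1−p)³.

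At p = 0.33, all ablated: 0.301 + 0.444 × 0.301 = 0.434. With one unablated: 0.449 + 0.442 × 0.301 = 0.582.

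| Assumed true DLT rate | All ablated | One unablated, half the risk | One unablated, zero risk |
|---|---|---|---|
| 10% | 0.906 | 0.924 | 0.941 |
| 20% | 0.709 | 0.756 | 0.804 |
| 33% | 0.434 | 0.508 | 0.582 |
| 50% | 0.172 | 0.242 | 0.312 |

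These figures are conditional on one missed MWA in the first three. To average over that, let each patient miss MWA with probability q and then carry a share s of the risk, so the effective rate is p(1−q) + s·p·q in both cohorts. At p = 0.33, P(pass) rises from 0.434 to 0.500 (q = 10%) or 0.570 (q = 20%) with s = 0, and to 0.467 or 0.500 with s = 0.5.

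**If such a patient is not counted.** Section 6.2.4 requires a DLT assessment thirty days after ablation for everyone at the level. A patient never ablated has no such date, so the condition cannot be met literally and the text gives no way forward.

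**The case against.** A reader might infer that the plan keeps these patients in and scores them as DLT-free. No section says so. Naming one exclusion does not settle how the rest are handled, and 6.2.4 can be read against it. For withdrawals, 6.8 may leave no end-of-window status to score. This stands: upward bias is one of two outcomes of the silence, and the other is a stalled level.

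A reader might also extend the point to every reason for missing MWA. That is too broad. A patient who misses MWA because of a qualifying SBRT toxicity already has a DLT. Patients whose dose constraints cannot be met continue off study (6.4.6). Some infeasibility found on imaging will be progression under 7.2.1.3 and so already covered.

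The mention of about 90 days after SBRT in 6.2.2 could be taken as a fallback end to the window. It reads as a description of the usual interval, and 7.1.1 and 9.3.1 omit it. If it were a fallback, it would lead to scoring the unablated patient as DLT-free. Section 13.4 concerns only how long SAEs are collected; it shows that a missed second procedure was foreseen, not how the DLT cohort is formed.

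Finally, DLTs are grade 4 or higher, so low true rates are plausible, and at 10% the shift is only 0.906 to 0.941. That is fair, and the table includes it. It does not remove the gap: the plan still needs one rule for who is counted.

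**Conclusion.** The point holds as a gap in the primary-endpoint denominator. The exclusion in 6.2.2 is too narrow by its own reasoning, and nothing in 6.2.4, 9.3.1, 9.4.1 or 13.5.1 closes it. As worded, it can also remove a genuine SBRT-attributable DLT.

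The bias toward escalation arises only if unablated DLT-free patients are counted. With one such patient in the first three at zero risk, the probability of passing a level rises by about 0.04 at a true rate of 10% (0.941 − 0.906), 0.10 at 20% (0.804 − 0.709), 0.15 at 33% (0.582 − 0.434) and 0.14 at 50% (0.312 − 0.172). At half the risk, the rise is about 0.07 at both 33% (0.508 − 0.434) and 50% (0.242 − 0.172). All these rates are assumed. The documents do not support the stronger conclusion that the reported MTD will be too high, because neither the handling nor the frequency of missed MWA is stated.

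**What to change.** In 6.2.2, 9.3.1, 9.4.1 and 13.5.1, define a DLT-evaluable patient as one who either has a DLT at any time from the start of SBRT, or receives MWA and completes the 30-day post-MWA assessment. Treat all others as non-evaluable, whatever the reason, and replace them, so that 0/3, 1/3 and 2/6 refer to evaluable patients. This also keeps in the count a progressor who has had a DLT. Change 6.2.4 to refer to all evaluable patients at the level. State whether the caps of 18 and 28 mean enrolled or evaluable. Report toxicity in all SBRT-treated patients separately, so that nothing seen in replaced patients is lost.

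The text change is a short amendment that restores the ordinary 3+3 probabilities in the all-ablated column. The operational cost is larger: each replacement adds one enrolment and roughly 12 weeks to MWA plus 30 days. Eighteen evaluable patients need 18/0.9 = 20 enrolled at an assumed 10% missed-MWA rate, or 18/0.8 = 22.5, so 23, at 20%. Accrual under 9.1.1.1 is 20% of 40-50, or 8-10 patients a year. Enrolling 18 therefore takes 1.8 to 2.25 years, and 20-23 takes 2.0 (20/10) to 2.9 (23/8) years, against a stated 1-2 years that also covers treatment and follow-up. The stated accrual time may need to lengthen.

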6.1 Overview

Patients will be referred to the study by their treating urologist. The urologist will determine the appropriateness for patient referral and discuss the option of study participation with their patients. After biopsy, patients will be treated on study with a course of SBRT treatment by a radiation oncologist. A 3+3 dose escalation scheme will be used. Four to six weeks after treatment, patients will be evaluated for microwave ablation by the treating radiologist with repeat imaging to ensure microwave ablation remains feasible. Two months after treatment, patients will be referred to an interventional radiologist for treatment with microwave ablation as well as repeat biopsy for exploratory analysis. Both SBRT and MWA will be administered on an outpatient basis. Details of treatment are as described below.

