7.1 Toxicity Assessment

- 7.1.1. Dose-limiting toxicity (DLT) will be defined as grade 4 non-hematologic/grade 5 toxicity attributable to treatment, occurring until 30 days after ablation. Patients will be monitored and assessed for unexpected long-term toxicity during the post-treatment followup period. In the case of unexpected long-term toxicity, the dose level will be evaluated and potentially used to recalculate the MTD. Potential toxicities due to stereotactic body radiation therapy and microwave ablation are listed in Section 13.1 and 13.2 respectively. The most likely acute side effects of treatment include fatigue, nausea, vomiting, and pain due to the procedure. Toxicities not caused by treatment, such as pain due to tumor progression, will be excluded from the assessment.

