9.3 Definition of end-points

- 9.3.1 Primary Endpoint of the Phase I study:

Dose-limiting toxicity (DLT) will be defined as grade 4 or higher non-hematologic toxicity attributable to treatment occurring until 30 days after ablation. This will exclude toxicities not caused by treatment, such as pain due to tumor progression. Toxicities will be defined per NCI CTCAE v5.0.

- 9.3.2 Secondary endpoints of the Phase I study:
 - 9.3.2.1 Local control: Radiologic response per RECIST criteria and volumetric measurements.
 - 9.3.2.2 Progression free survival defined with follow-up radiological assessment with progression free survival (PFS) calculated from the point of start of SBRT to the point of recurrence or death.
 - 9.3.2.3 Overall survival (OS) defined from the point of start of SBRT to the time of death or last follow-up if alive.
 - 9.3.2.4 Tumor pathology: H&E staining and pathologic evaluation for percentage of viable tumor remaining as measured by the presence of necrosis, fibrosis, hyalinization, and/or calcification, compared to pre-SBRT pathology.

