9.4 Statistical Analysis

- 9.4.1 Primary objective of Phase I study:

A 3+3 design will be utilized for dose escalation. For each three patient cohort, DLT will be assessed as above. In the case of 0/3 DLTs, the dose will be escalated to the next level. In the case of 2/3 DLTs, the trial will be terminated with the previous level being the MTD. In the case of 1/3 DLTs, an additional three patients will be enrolled at the current dose level. If no additional DLTs are seen, the dose will be escalated to the next level. In the event of a total of 2 or more DLTs in 6 patients, the trial will be terminated with the previous dose level being the MTD. Toxicities will be tabulated by type and grade.

- 9.4.2 Secondary objectives of Phase I study:

- 9.4.2.1 Local control will be reported actuarially as a percentage with an associated 95% exact confidence interval.
- 9.4.2.2 Progression free and overall survival will be estimated using the Kaplan-Meier method. For calculation of PFS, patients without recurrence and alive at last follow-up will be censored at the date of the last radiologic assessment. For calculation of OS, patients alive at last follow-up will be censored. Log-rank test and Cox regression analysis will be used for univariate and multivariate analyses, respectively. Chi-square and regression analysis will be performed to test association of categorical variables with treatment response.
- 9.4.2.3 Tumor response will be reported via rates of complete response, partial response, and no response.

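### The exclusion of progressors in section 6.2.2 can remove a dose-limiting toxicity that has already been observed from the 3+3 count

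*Combined protocol and SAP*

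**What the plan says.** Section 6.2.2 counts listed events of grade 4 or higher, up to 30 days after MWA, when they are "attributable to the radiation, the MWA or the combination of the treatment". Ablation is therefore not needed for an event to qualify. Section 7.1.1 ("grade 4 non-hematologic/grade 5 toxicity attributable to treatment, occurring until 30 days after ablation") and section 9.3.1 ("grade 4 or higher non-hematologic toxicity attributable to treatment occurring until 30 days after ablation") close the window at the same point, so both cover the weeks between SBRT and ablation.

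Section 6.2.2 then sets an exclusion. The condition is "If progressive disease is found at the time of interval imaging and the patient is deemed ineligible for MWA", and the consequence is that "the patient will not be part of the cohort used for DLT analysis as his/her inclusion may falsely lower potential toxicity rates". Section 6.1 gives the timing of that imaging: "Four to six weeks after treatment, patients will be evaluated for microwave ablation by the treating radiologist with repeat imaging".

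Under section 6.2.3, 0/3 DLTs escalates, 1/3 adds three patients, and 2/3 or at least 2/6 halts with the previous level as the MTD. Section 9.4.1 applies the same rule ("For each three patient cohort, DLT will be assessed as above"), and section 13.5.1 repeats its halting and expansion steps. None of sections 7.1.1, 9.3.1, 9.4.1 and 13.5.1 mentions the exclusion.

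**The concern.** The exclusion has two conditions, progression and ineligibility for MWA. Neither depends on whether the patient has already had a DLT, and the whole patient is removed. The stated reason holds only for a DLT-free patient, whose unablated follow-up would dilute the rate. For a patient who has had a DLT the effect is reversed: removal lowers the count.

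Section 6.2.2 also does not require the ineligibility to result from the progression. Section 6.9.3 lists a DLT as a ground for withholding treatment, so a DLT could contribute to the removal of its own patient.

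Counts of 0, 1 or 2 drive every escalation decision and the MTD. What is at stake is an observed event of grade 4 or higher that does not enter the decision to open the next dose level.

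Three limits apply. Leaving out DLT-free progressors is sound. A patient who misses MWA because of a DLT, without progression, is not removed by this sentence. The lack of cross-references elsewhere is a gap, not a contradiction.

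**Working it through.** **The plan's own figures.** Three levels of 3 patients give 9, three levels of 6 give 18, and 18 + 10 = 28. These match the Phase IA range and the overall maximum.

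**Inputs.** The 3+3 rule, the exclusion and the imaging time come from the protocol. It gives no DLT or progression rates and the visible text states no replacement rule, so all rates below, and replacement of an excluded patient, are assumptions.

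- s = DLT rate in the SBRT phase; a = DLT rate in the MWA phase; p = s + (1−s)a.
- s = 0.05, a = 0.10: p = 0.05 + 0.95×0.10 = 0.145.
- s = a = 0.20: p = 0.20 + 0.80×0.20 = 0.36.
- The chance that a level passes is f(p) = (1−p)³ + 3p(1−p)⁵, so f(0.145) = 0.824 and f(0.36) = 0.378.

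**1. Direction.** Replacing a patient with a DLT puts a 0 or a 1 where a 1 stood. Neither the three-patient nor the six-patient count can rise. Unless the replacement also has a DLT, 1/3 (expand) becomes 0/3 (escalate), 2/3 (halt) becomes 1/3 (expand), and 2/6 (halt) becomes 1/6 (escalate).

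**2. When it happens.** Take one DLT in the first cohort, with the other two patients DLT-free, and write q = 1−p. If the DLT counts, the cohort is 1/3 and passes with probability q³. If it is dropped and the patient replaced, the level escalates at once with probability q and passes with probability q + p·q³.

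| Assumed s / a | Escalates at once if dropped | Passes if counted | Passes if dropped |
|---|---|---|---|
| 5% / 10% | 0.855 | 0.625 | 0.855 + 0.145×0.625 = 0.946 |
| 20% / 20% | 0.640 | 0.262 | 0.640 + 0.36×0.262 = 0.734 |

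Without conditioning on the other two patients, the comparison is f(p) if dropped against (1−p)⁵ if counted: 0.709 against 0.328 at p = 0.2, 0.494 against 0.168 at p = 0.3, and 0.309 against 0.078 at p = 0.4.

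**3. How often.** If a share g of patients with an SBRT-phase DLT progress and are deemed ineligible, a patient has a dropped DLT with probability d = s·g. The chance of at least one among n patients is 1−(1−d)ⁿ.

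| s | g | d | n = 9 | n = 18 |
|---|---|---|---|---|
| 0.05 | 0.1 | 0.005 | 0.044 | 0.086 |
| 0.05 | 0.2 | 0.010 | 0.086 | 0.165 |
| 0.05 | 0.3 | 0.015 | 0.127 | 0.238 |
| 0.01 | 0.1 | 0.001 | 0.009 | 0.018 |
| 0.01 | 0.3 | 0.003 | 0.027 | 0.053 |

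**4. Average effect of the current rule.** Let x₁ and x₀ be the exclusion probabilities with and without an SBRT-phase DLT. The DLT rate among counted patients is [s(1−x₁) + (1−s)(1−x₀)a] / [s(1−x₁) + (1−s)(1−x₀)]. If x₁ = x₀, this equals p and nothing changes. If every progressor with a DLT but only half of the DLT-free progressors are excluded, then at 10%, 20% and 30% progression f moves from 0.824 to 0.828, 0.833 and 0.839 (5%/10%), or from 0.378 to 0.391, 0.405 and 0.422 (20%/20%).

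**The case against.** The strongest reply is that the sentence states its own purpose. Read with that purpose it reaches only DLT-free patients, and an investigator would count the event anyway. Section 6.2.4 also holds the next level until DLT status has been evaluated for everyone at the current one, and sections 7.1.1 and 9.3.1 define the endpoint without excluding progressors. This is a fair reading of intent. But none of these sections overrides an exclusion written without exception, and a primary-endpoint rule should not depend on being read against its wording.

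The second reply is rarity. Section 13.1 lists most of the SBRT events that 6.2.2 names as DLTs among rare, late effects. To be dropped, one must reach grade 4 by about the time of imaging, in a patient who also progresses and is deemed ineligible. SBRT-phase rates of 5%, and still more 20%, may therefore be too high; the 1% rows above give 1–3% in 9 patients and 2–5% in 18. This stands and limits the frequency.

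Third, the event would not go unseen. SAE reporting in 13.4, and disease-group and committee review in the data safety monitoring plan, would pick it up, and the committee can act to suspend the study. That also stands, but none of it enters the 3+3 count.

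Fourth, the large probabilities condition on the event having happened and on replacement. Without replacement the cohort is 0/2, for which 6.2.3 gives no action. On average the current rule is unbiased under independence, whereas the remedy is not. The case for the change therefore rests on safety and on using every observed DLT, not on lower average bias.

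**Conclusion.** The concern holds. As written, section 6.2.2 can remove an observed, qualifying DLT from the 3+3 count, against its own stated reason, and no other section expressly restores it. The fault lies in individual cases. When it occurs, the decision can only stay the same or become less strict; in the worked case the chance that the level passes rises from 0.625 to 0.946, or from 0.262 to 0.734. The average effect is zero if exclusion is independent of DLT status, and at most 0.044 (0.378 to 0.422) in the dependent scenarios examined. The documents support none of the assumed rates, and the event is probably uncommon. It should be fixed because the decision concerned is whether to expose new patients to a higher dose.

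**What to change.** Limit the exclusion in 6.2.2 to patients without a qualifying DLT, for example:

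> A patient who has a qualifying DLT at any time from the first SBRT fraction counts in the DLT analysis, whether or not there is progression and whether or not MWA is given. A patient without a DLT who progresses and is deemed ineligible for MWA is not evaluable for DLT and is replaced at the same level.

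Refer to this rule from 7.1.1, 9.3.1, 9.4.1 and 13.5.1. Two clarifications are useful but secondary. State whether replaced patients count toward the 18 in 6.2.4 ("Dose escalation/de-escalation will continue until a maximum of 18 patients are accrued"). State also when the window closes for a patient who is never ablated: 7.1.1 and 9.3.1 tie it to ablation, and only 6.2.2 adds an approximate interval of 90 days after SBRT.

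The cost is one or two sentences, occasional replacement patients, and a conservative lean, because DLTs in unablated patients count while DLT-free unablated patients do not. With a share m of DLT-free patients not ablated, the counted rate is [s + (1−s)(1−m)a] / [s + (1−s)(1−m)], and the chance that a level passes becomes:

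| s / a | All ablated | m = 10% | m = 20% | m = 30% |
|---|---|---|---|---|
| 5% / 10% | 0.824 | 0.814 | 0.803 | 0.787 |
| 20% / 20% | 0.378 | 0.353 | 0.325 | 0.292 |

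In the dependent scenario at 30% progression (m = 15%), the fix gives 0.340 and the current rule 0.422 around 0.378; at 5%/10% they are 0.809 and 0.839 around 0.824. The errors there are similar in size and opposite in direction. The fix errs toward safety and discards no observed DLT.

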9.1.2 Phase IB – Ten (10) patients

9.1.2.1 An additional ten patient, Phase IB expansion cohort will be accrued at the MTD at the conclusion of the Phase IA study to obtain further assessments of safety and provide preliminary estimates of local control rates to inform a potential Phase II study.

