13.5 Stopping Rules

13.5.1 As described above, the study will use a standard 3+3 dose escalation design. For each three patient cohort, DLT will be assessed as above. In the case of 2/3 DLTs, the trial will be terminated with the previous level being the MTD. In the case of 1/3 DLTs, an additional three patients will be enrolled at the current dose level. In the event of a total

of 2 or more DLTs in 6 patients, the trial will be terminated with the previous dose level being the MTD.

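### Phase IB is meant to validate the Phase IA MTD, but no stated DLT count pauses its accrual or revises the MTD

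*Combined protocol and SAP*

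**What the plan says.** Section 6.2.3 sets the Phase IB dose: "Once the MTD has been established, the MTD will be used for the subsequent Phase IB expansion cohort". Section 6.2.4 gives the ten extra patients their purpose, "to validate the results of phase-IA and provide a preliminary assessment of efficacy", and 9.1.2.1 says the "expansion cohort will be accrued at the MTD at the conclusion of the Phase IA study to obtain further assessments of safety". The synopsis calls Phase IB optional.

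The numerical DLT rules appear in three places.

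- **6.2.3:** 0/3 escalates, 2/3 halts, and 1/3 adds three patients. After 1/3, "If no additional DLTs are seen, the dose will be escalated to the next level"; 2 or more in 6 halts, with the previous level as the MTD.
- **9.4.1:** repeats this, introduced by "For each three patient cohort, DLT will be assessed as above".
- **13.5.1 (Stopping Rules):** repeats the halting part, introduced by "As described above, the study will use a standard 3+3 dose escalation design".

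The wait for 30-day post-ablation DLT results is in 6.2.4, where "accrual in the phase-IA study will be done in groups of three patients". The one sentence on revising the MTD is in 7.1.1: "In the case of unexpected long-term toxicity, the dose level will be evaluated and potentially used to recalculate the MTD". Section 6.9.3 withholds treatment from an individual patient after a DLT.

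**The concern.** A validation cohort needs a result that would count as failure, and none is stated. Two DLTs in six patients reject a dose in Phase IA. The same or a worse rate in Phase IB has no prescribed consequence, either for accrual or for the reported MTD.

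This matters because determining the MTD is the primary objective and Phase IA leaves it imprecise. The visible rules let a level pass on 0/3 or on 1/6, with exact 95% intervals for the DLT rate of 0-71% and 0.4-64%. A DLT is a grade 4 or higher event such as haemorrhage or bowel perforation, in medically inoperable patients. Without a rule, when to pause depends on case-by-case judgement, and the trial could report an MTD whose pooled DLT rate is higher than the rate that rejects a dose during escalation.

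**Working it through.** **The plan's own figures.** Three levels × 3 = 9; three levels × 6 = 18; 18 + 10 = 28. These match 9.1.1 and 6.2.4.

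**Does any count rule reach Phase IB?** Each rule is expressed per three patients, or six after expansion, and its consequence is that the previous level becomes the MTD. Phase IB is a single ten-patient cohort entered after the MTD is set. The rules say nothing about, for example, 3/8 or 5/13. The text of 7.1.1 concerns long-term toxicity, not events within 30 days of ablation.

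**Inputs assumed.** The documents give no DLT rates. Three curves for levels I-III are used: 5/10/20%, 10/20/30% and 20/40/50%.

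**Chance a level passes.** With q = 1 − p, a level passes on 0/3 with probability q³ and on 1/6 with probability 3pq²·q³. At p = 0.2: 0.512 + 0.197 = 0.709. At p = 0.4: 0.216 + 0.093 = 0.309. At p = 0.5: 0.125 + 0.047 = 0.172.

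**Chance a level is declared the MTD.** This is P(lower levels pass) × P(this level passes) × P(next level fails). The last factor is 1 for level III; the visible text does not define the MTD when all three levels pass.

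**When the pooled rate ends above 1/3.** From 0/3, five or more DLTs in ten are needed (5/13 = 38%; 4/13 = 31%). From 1/6, also five or more (6/16 = 37.5%; 5/16 = 31%). P(X ≥ 5 of 10) is 0.033, 0.150, 0.367 and 0.623 at p = 0.2, 0.3, 0.4 and 0.5.

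**Worked example, 20/40/50%.**
- Level I: 0.709 × (1 − 0.309) = 0.489; × 0.033 = 0.016.
- Level II: 0.709 × 0.309 × (1 − 0.172) = 0.18; × 0.367 = 0.067.
- Level III: 0.709 × 0.309 × 0.172 = 0.038; × 0.623 = 0.023.
- Levels I-II: 8.3%. All three: 10.6%.

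| Assumed curve | MTD at I-II | MTD at I-III | I-III, if the unseen figure fills the MTD to six with step-down |
|---|---|---|---|
| 5/10/20% | 0.04% | 2.1% | 1.3% |
| 10/20/30% | 1.1% | 5.9% | 4.1% |
| 20/40/50% | 8.3% | 10.6% | 7.3% |

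**Behaviour of a pooled boundary.** The boundary pauses at 2 DLTs among the first six patients at the dose, then at 3/7-9, 4/10-12, 5/13-15 and 6/16. Checked in order of entry, the pause probability is 0.038, 0.172, 0.385, 0.617 and 0.809 at p = 0.1, 0.2, 0.3, 0.4 and 0.5. It is the same from 0/3 as from 1/6, because 1/6 starts one DLT and three patients further along the same boundary.

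**Timing at p = 0.4.** The 0.617 splits by Phase IB patient as 0.160 (2nd), 0.192 (3rd), 0.069 (5th), 0.097 (6th), 0.040 (8th) and 0.060 (9th). About 0.10 comes at the eighth or ninth patient, too late to spare many; about 0.52 is useful. Given a useful pause, the mean number of patients after the triggering one is (0.160×8 + 0.192×7 + 0.069×5 + 0.097×4)/0.518 = 6.5.

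The DLT window is 2 weeks + 8 weeks + 30 days, about 14.3 weeks. At 20% of 40-50 patients, 8-10 enter a year, so 2-3 enter during one window. Without an accrual hold, a useful pause therefore leaves about 3.5 to 4.5 of the ten not yet entered.

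**The case against.** The strongest reply is that individual review is already mandatory. A DLT is grade 4 or higher, so it would ordinarily be a serious event under the 24-hour reporting in 13.4. Under the data safety monitoring plan (Appendix 2) it reaches the DSMC Chair within one business day, and the Chair must decide whether immediate action is needed. Disease-group meetings discuss dose adjustments, the DSMC can suspend or close the study, and 9.5.1 requires a safety analysis after accrual, before any Phase II. A pooled rate above 1/3 needs at least five Phase IB DLTs, each passing through that review. This stands, and it limits the severity. It does not supply a criterion: no layer states a DLT count or says when the MTD changes.

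A reader might infer that nothing can stop Phase IB. The documents do not support that; the gap is the missing DLT criterion only.

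It can also be said that 13.5.1 speaks of the study as a whole and of terminating the trial. That is an ambiguity, but its counts and its consequence fit escalation cohorts, not a ten-patient expansion.

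The 3+3 figure is not shown and may already fill the MTD to six. That would lower the probabilities and make one part of the fix unnecessary. It would not create a Phase IB count.

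Finally, the gain is modest. On the 20/40/50% curve, level II (40%) is the MTD with probability 0.18, so a useful pause there has probability about 0.18 × 0.52 = 0.09. Level I (20%) is the MTD with probability 0.49, so pausing that dose has probability about 0.49 × 0.17 = 0.08. This stands too, but a pause leads to review, not automatic closure.

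**Conclusion.** The point holds and should be fixed, at modest severity. As visibly written, the MTD may rest on 0/3 or 1/6, ten more patients may enter with no prescribed hold, and their DLTs have no stated effect on the MTD.

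The better guide to size is the levels I-II range, 0.04% to 8.3%, because it does not rely on treating level III as an MTD. A reader might take 10.6% as the risk that the trial endorses too toxic a dose. The documents do not support that: the figure needs the steepest assumed curve, counts level III, and assumes all ten patients are treated with no DSMC action. On the two lower curves most of the I-III figure comes from level III. The textual gap depends on none of these assumptions; its numerical size depends on all of them. Confidence is medium.

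**What to change.** Amend 6.2.4 and 13.5.

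- **(a) Pooled boundary.** Pool Phase IA and IB DLTs at the MTD. Pause Phase IB accrual for DSMC review as soon as there are 2 DLTs among the first six evaluable patients at that dose, and after that whenever the pooled rate reaches 1/3 (3/7-9, 4/10-12, 5/13-15, 6/16). The investigators may set another boundary, provided it is written down.
- **(b) Completing six.** If the MTD rests on only three patients and the 3+3 figure does not already fill to six, apply the 2-in-6 criterion and the 30-day post-ablation hold to the first three Phase IB patients. State what follows a failure: the remaining patients move to the lower level under the same rule, or Phase IB closes.
- **(c) Final MTD.** Base the final MTD statement on all patients treated at that dose.

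The change is protocol wording within the planned ten patients. Its cost is a possible pause of about 14 weeks, and a second if the dose fails at six, on top of the 12-15 months that ten patients take at 8-10 a year. A dose with a true 20% DLT rate would be paused with probability about 0.17. If the dose fails at six, fewer patients remain for the final dose.
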